4.2 METHOD OF TREATMENT ASSIGNMENT AND BLINDING

4.2.1 Randomization and Blinding

This study is randomized, double-blinded, and placebo-controlled to minimize potential bias in treatment assignment, patient monitoring, and efficacy assessments. Random allocation will be conducted via an interactive voice or web-based response system (IxRS) and the Sponsor will provide the specifications of the randomization algorithm to the IxRS vendor. Patients in Cohort 1 will be randomly allocated to 200 mg PO BID fenebrutinib or placebo at an approximately 2:1 ratio using a stratified permuted blocks randomization scheme with stratification by country. Patients in Cohort 2 will be

randomly allocated to each of the four treatment arms at an approximately 1:1:1:1 ratio, using a stratified permuted blocks randomization scheme with stratification by country.

Patients and study site personnel will be blinded to the individual treatment assignments throughout the study. Only standard and safety laboratory data results from the local laboratory (such as CBC, chemistries, and pregnancy testing) will be available to sites. Results of other assessments performed after randomization that might unblind investigators to the treatment patients received will not be provided to sites or to the Sponsor's staff directly involved in study conduct. [REDACTED]

Although PK samples must be collected from patients assigned to the comparator arm to maintain the blinding of treatment assignment, PK assay results for these patients are generally not needed for the safe conduct or proper interpretation of this trial. Sponsor personnel or a designee responsible for performing PK assays will be unblinded to patients' treatment assignments to identify appropriate PK samples to be analyzed. Samples from patients assigned to the placebo arm will not be analyzed except by request (e.g., to evaluate a possible error in dosing).

Patient and study site personnel will be blinded to treatment assignments throughout the study. During trial conduct, the Sponsor will monitor blinded clinical and safety data on safety and study conduct on an ongoing basis. For Cohort 1, if required for safety evaluations, Sponsor team personnel, but not the sites, not directly involved in the conduct of the study will have access to unblinded data. These Sponsor team personnel may include individuals with clinical and medical experience, biostatisticians, and individuals responsible for analyzing and interpreting the pharmacodynamics and pharmacokinetics of the study drug. For information on Cohort 2, see Section 3.1.1.

4.2.2 Unblinding

If unblinding is necessary for patient management (e.g., in the case of a serious adverse event for which patient management might be affected by knowledge of treatment assignment), the investigator will be able to break the treatment code by contacting the IxRS. Treatment codes should not be broken except in emergency situations. If the investigator wishes to know the identity of the study drug for any other reason, he or she should contact the Medical Monitor directly. The investigator should document and provide an explanation for any premature unblinding (e.g., accidental unblinding, unblinding due to a serious adverse event).

For regulatory reporting purposes, and if required by local health authorities, the Sponsor will break the treatment code for all serious, unexpected, suspected adverse reactions (see Section 5.7) that are considered by the investigator or Sponsor to be related to study drug.

4.3 STUDY TREATMENT

The investigational medicinal product (IMP) for this study is fenebrutinib.

4.3.1 Formulation, Packaging, and Handling

4.3.1.1 Fenebrutinib and Placebo

Fenebrutinib will be provided by the Sponsor as 50-mg dose strength tablets with corresponding matching placebo tablets, which will be indistinguishable in appearance. Study drug (fenebrutinib or placebo) will be dispensed at the Day 1 and 29 visits for both cohorts.

Tablets will be supplied in bottles (Cohort 1) and blister wallets (Cohort 2) for the treatment arm to which the patient is randomly allocated. Each bottle and blister wallet will be labeled per local regulatory requirements. Fenebrutinib and placebo tablets should be stored between 2°C and 8°C. Please refer to the pharmacy manual for detailed instructions on study drug storage and preparation.

For information on the formulation and handling of fenebrutinib, see the Fenebrutinib Investigator's Brochure.

4.3.1.2 *Background Therapy: Standard-of-Care H1 Antihistamines for CSU*

For information on the formulation, packaging, and administration of standard-of-care H1 antihistamines for CSU, see local prescribing information.

4.3.2 Dosage, Administration, and Compliance of Fenebrutinib and Placebo

4.3.2.1 Fenebrutinib and Placebo Dose and Administration

For Cohort 1, the fenebrutinib dose level is 200 mg (4 tablets) BID (total of 8 tablets each day) with matching placebo (see Section 3.1). For Cohort 2, the fenebrutinib dose levels are 50 mg QD, 150 mg QD, and 200 mg BID, with matching placebos (see Table 3).

Patients in both cohorts will take fenebrutinib/placebo on Day 1 and ending on the Day 56 visit. Although *the Day 57 visit* is the last day of the study treatment period, no study drug for Study GS39684 will be given on *the Day 57 visit*. *If eligible, patients may enroll into the OLE Study GS40868 to receive their first open-label dose of fenebrutinib on Day 1 of the OLE or they will proceed and return for the safety follow-up visit 4 weeks after the last dose of study drug. For patients enrolling into the OLE, Day 1 of Study GS40868 may be the same day as the Day 57 visit in Study GS39684.*

For mandatory morning clinic visits (see Appendix 1 and Section 4.4.5), patients should be instructed that the morning dose of study drug will be taken in the clinic. On other clinic visit days, if the visit occurs in the morning, the patient should be instructed that the morning dose of study drug will be taken in the clinic.

Table 3 Fenebrutinib Dosing Regimen by Treatment Arm (Cohort 2)

| Fenebrutinib Dose Arm | Number of Tablets | |
|-----------------------|-----------------------------|------------------------|
| | Fenebrutinib (a.m./p.m.) | Placebo (a.m./p.m.) |
| 50 mg QD | 1/0 | 3/4 |
| 150 mg QD | 3/0 | 1/4 |
| 200 mg BID | 4/4 | 0/0 |
| Placebo | 0/0 | 4/4 |

BID=twice daily; QD=once daily.

Fenebrutinib or placebo may be taken orally with or without food, except on certain days (see [Appendix 1](#)), when the morning dose of oral study drug will be administered at the morning (mandatory) clinic visit while fasting. The dates and times of the most recent prior meal, last dose of oral study drug (prior to clinic visit), and timing of oral study drug administration in clinic should be recorded at each clinic visit. Patients should be instructed that a missed dose should not be taken with the next scheduled dose.

In addition, any antacids (e.g., Pepto-Bismol[®], Roloids[®]) should be recorded as concomitant medications, including date and time of last administration. Administration of study drug should be staggered with antacid use (i.e., study drug should be taken 2 hours before or 2 hours after the antacid).

At the Day 1 and 29 visits, sufficient study medication tablets will be dispensed to complete dosing until the end of the study. When study medication is administered at the site, it will be administered under supervision of study personnel, and the amount of study medication dispensed must be recorded.

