4.3.2.2 Fenebrutinib and Placebo Compliance

The following measures will be taken to assess patient compliance with study drug. For Cohort 1, patients will be directed to bring the study drug bottle to each visit after randomization. In addition, sites will be responsible for prepopulating the dates on the dosing label (affixed to the bottle) for when patients are scheduled to take study drug. The patients will record the times (a.m. or p.m.) that they take each dose in their eDiary. The number of tablets issued minus the number of tablets returned will be used to calculate the number of tablets taken and compliance.

For Cohort 2, sites will be responsible for prepopulating the dates on the blister wallets for when patients are scheduled to take study drug. The patients will record the times (a.m. or p.m.) that they take each dose in their eDiary. Patients will be instructed to return all blister wallets (used and unused) at each study visit for assessment of compliance and for medication disposal.

Compliance will be documented on the source record. Any overdose or incorrect administration of study drug should be noted on the Study Drug Administration electronic

Case Report Form (eCRF). Adverse events associated with an overdose or incorrect administration of study drug should be recorded on the Adverse Event eCRF. If compliance is $\leq 80\%$, the investigator or designee is to counsel the patient and ensure steps are taken to improve compliance.

4.3.2.3 *Background Therapy: Standard-of-Care H1 Antihistamines for CSU*

The following H1 antihistamine medications are allowed:

- *Cetirizine 10–40 mg QD*
- *Levocetirizine 5–20 mg QD*
- *Fexofenadine 180–720 mg QD*
- *Loratadine 10–40 mg QD*
- *Desloratadine 5–20 mg QD*
- *Rupatadine 10–40 mg QD*
- *Bilastine 20–80 mg QD*

All patients will be allowed to take study-defined, second-generation, H1 antihistamine medications consistent with standard-of-care (i.e., up to 4 times the approved dose per local treatment guidelines) during the screening, treatment, and follow-up periods. Patients should remain on a stable H1 antihistamine regimen throughout the study period. Loratadine (10 mg) or cetirizine (10 mg) will be provided and used on an as-needed basis (maximum 1 per day) during screening, treatment, and follow-up periods). Therapies used for the treatment of CSU prior to enrollment will be collected as part of the patient’s medical history.

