4.4.2 Cautionary Therapy

4.4.2.1 Acid-Reducing Agents

Patients who use antacids (e.g., Pepto-Bismol[®], Rolaid[®]) for symptomatic relief of heartburn should take fenebrutinib or matching placebo at least 2 hours before or 2 hours after antacid administration because gastric acid improves fenebrutinib absorption.

Patients may be treated with PPIs or H2RAs at up to the maximum recommended dose according to local labeling. The dose should remain stable for at least the 2 weeks before randomization and throughout the study.

At visits with scheduled PK assessments (see [Appendix 1](#)), any use of PPIs, H2RAs, and/or other antacids (e.g., Pepto-Bismol[®], Roloids[®]) should be recorded as concomitant medications, including the date and time of last administration.

4.4.2.2 *Statins*

Several lipid-lowering agents (statins) are metabolized by CYP3A (simvastatin, lovastatin) and/or transported by BCRP (rosuvastatin, atorvastatin), and thus may be affected by drug-drug interaction with fenebrutinib, therefore, dose adjustments of these medications should be considered (Kellick et al. 2014).

- *Simvastatin: recommended maximum dose of 10 mg/day*
- *Lovastatin: recommended maximum dose of 20 mg/day*
- *Rosuvastatin: recommended maximum dose of 10 mg/day*
- *Atorvastatin: recommended maximum dose of 20 mg/day*

The use of statins has been associated with myopathy, which can manifest as weakness, tenderness or muscle pain with elevations of creatine kinase (CK) above ten times the ULN. In severe cases, myopathy can cause rhabdomyolysis with or without acute kidney injury secondary to myoglobinuria, and rare fatalities due to rhabdomyolysis have occurred. The risk of myopathy is increased by elevated plasma levels of statins. Predisposing factors for myopathy include advanced age (≥ 65 years), female gender, uncontrolled hypothyroidism, renal impairment, or the use of concomitant medications that increase the plasma levels of the statin.

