| Fenebrutinib/placebo administration in clinic ^{q, r} | | | x | x | x | x | | | | | |
| Drug Dispensing | | | x | | | x | | | | | |
| Hematology ^s | x | x | x | x | x | x | | x | x | x | x ^k |
| Chemistry ^t | x | x | x | x | x | x | | x | x | x | x ^k |
| Fasting Lipid Panel | | | x | | | x | | x | x | | |
| Coagulation studies ^u | x | | | | | | | | | x | x ^k |
| Pregnancy test ^v | x | | x | x | x | x | | x | x | x | |
| Urinalysis ^w | x | | x | | | | | x | x | x | |
| | | | | | | | | | | | |
| FricTest (for patients with dermographism only) | x | | x | | | | | x | x | x | |
| Plasma PK assessment ^y | | | x | x | | | | x | | x | x ^k |
| | | | | | | | | | | | |
| Phone call ^{bb} | | | | | | | x | | | | |

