Appendix 1 Schedule of Activities (Cohorts 1 and 2) (cont.)

BID=twice a day; eCRF=electronic case report form; eDiary=electronic diary (patient reported outcomes); HBcAb=hepatitis B core antibody; HBsAb=hepatitis B surface antibody; HBsAg=hepatitis B surface antigen; HCV Ab=hepatitis C antibody; *OLE* = *open-label extension*; PD=pharmacodynamic; PK=pharmacokinetic; PPD= purified protein derivative; PPI=proton pump inhibitor; QFT= QuantiFERON-TB Gold®; QTcF=QT interval corrected using Fridericia's formula; TB=tuberculosis; [REDACTED] Term.=Termination; UAS=Urticaria Activity Score; UAS7=Urticaria Activity Score over 7 days; [REDACTED]

- a Laboratory tests prior to randomization and dosing may be performed locally on Day 0, if central laboratory tests are not available due to sampling handling problems, breakage, or lab error.
- b Safety follow-up visit 4 weeks after the last dose of study drug if the patient discontinues the study and/or study treatment (per Sections 4.6.1 and 4.6.2) prior to Day 85 visit or do not enter the OLE.
- c Phone call instead of a clinic visit.
- d Morning clinic visit is required for visits on Days 1, 8, 29, 57, and 85; for other study visits, morning visits are recommended. For mandatory morning visits, the patient should be fasting (overnight, > 8 hours) prior to the first PK blood draw and/or fasting lipid panel.
- e Day 57 visit is the last day of the study treatment period; however, no study drug will be taken at the Day 57 visit. The last dose of blinded study drug will be the p.m. dose on Day 56 or the day before the Day 57 visit if it does not occur on Day 57. *If eligible, patients may enroll into the OLE study to receive their first open-label dose of fenebrutinib on Day 1 of Study GS40868 or they will proceed and return for the safety follow-up visit 4 weeks after the last dose of study drug. For patients enrolling into the OLE study, Day 1 of Study GS40868 may be the same day as the Day 57 visit in Study GS39684.*
- f Patients should be trained to use the eDiary at Day -14. At Day -7, staff should query patients for any questions they may have concerning the use of the eDiary and ensure patients understand correct usage before randomization.
- g Patient is to complete the eDiary twice daily, approximately every 12 hours (a.m./p.m.), every day for the duration of the study. The eDiary includes the UAS7 (itch score, number of hives) and other patient reported outcomes.
- [REDACTED]

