- ^q On mandatory morning clinic visit days *during the treatment period* (Days 1, 8, 29, and 57), patients should be instructed that the morning dose of study drug will be taken in the clinic. On other clinic visit days, if the visit occurs in the morning, the patient should be instructed that the morning dose of study drug will be taken in the clinic. The morning dose should be taken after all pre-dose assessments are complete (i.e., ECG, questionnaires, and PK and ██████████ sample collection).
- ^e Patients will take fenebrutinib/placebo BID approximately every 12 hours starting on Day 1 and ending on Day 56 (pm) or the day before (pm) the Day 57 visit if it does not occur on Day 57. One dose (a total of 4 tablets) of fenebrutinib/placebo should be taken with water by mouth BID (a total of 8 tablets each day). The dates and times of the most recent prior meal, last dose of oral study drug (prior to clinic visit), and timing of study drug administration in clinic should be recorded at each clinic visit.
- ^s Includes WBC count, RBC count, hemoglobin, hematocrit, platelet count, and WBC differential (i.e., neutrophils, eosinophils, basophils, monocytes, lymphocytes, and other cells if present).
- ^t Includes sodium, potassium, chloride, bicarbonate, glucose, BUN or urea, creatinine, total protein, albumin, phosphorus, calcium, total and direct bilirubin, alkaline phosphatase, ALT, AST, uric acid, LDH, CRP, and lipase.
- ^u Includes PT, PTT, INR, and fibrinogen.
- ^v All women of childbearing potential, including those who have had a tubal ligation, will have a serum pregnancy test at screening. Urine pregnancy tests will be performed locally at specified subsequent visits. If a urine pregnancy test result is positive, it must be confirmed by a serum pregnancy test (performed locally).
- ^w Includes dipstick, including pH, specific gravity, glucose, protein, ketones, blood, and microscopic examination (e.g., sediment, RBCs, WBCs, casts, crystals, epithelial cells, bacteria if present).

Appendix 1
Schedule of Activities (Cohorts 1 and 2) (cont.)

■ [REDACTED]

y Collect PK samples prior to drug administration, and the patient should be fasting overnight for > 8 hours.

■ [REDACTED]

■ [REDACTED]

^{bb} Site staff to remind patients to take the study drug and to complete their eDiaries.

Appendix 2

Childbearing Potential, Pregnancy Testing, and Contraception

For Women

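### Does the plan fail to capture when the last active dose was taken before the pharmacokinetic samples in the two once-daily arms?

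*Combined protocol and SAP*

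**What the plan says.** Section 4.3.2.1 asks the site to record, at each clinic visit, the date and time of the last meal, of the last study-drug dose before the visit, and of any dose given in clinic; on the two doses it says that the "last dose of oral study drug (prior to clinic visit), and timing of oral study drug administration in clinic should be recorded". The dosing footnote in Appendix 1 repeats this: "and timing of study drug administration in clinic should be recorded at each clinic visit". Dosing times are approximate: "Patients will take fenebrutinib/placebo BID approximately every 12 hours starting on Day 1".

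The visible schedule in Appendix 1 places pharmacokinetic samples on Days 1, 8 and 57, at early termination and, optionally, at unscheduled visits. They are drawn before dosing. For Day 57, footnote e adds: "The last dose of blinded study drug will be the p.m. dose on Day 56", or the evening before the visit if it falls on another day.

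Table 3 gives the fenebrutinib tablets (a.m./p.m.) as 1/0 in the 50 mg QD arm, 3/0 in the 150 mg QD arm and 4/4 in the 200 mg BID arm. Placebo tablets bring every slot to four.

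There is a second record of dosing. Section 4.3.2.2 states, for each cohort: "The patients will record the times (a.m. or p.m.) that they take each dose in their eDiary". Section 4.5.9.1 lists study medication compliance as part of the eDiary. Section 4.3.2.2 also names a Study Drug Administration eCRF.

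Section 6.6 tabulates plasma concentrations by visit with descriptive statistics. Section 3.3.5 says the pre-dose samples also serve exposure and exposure-response analyses, which may be reported separately.

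**The concern.** A rule that records one pre-visit dose suits a regimen in which every dose is active. That was so for the fenebrutinib arm of Cohort 1. In Cohort 2 the same rule yields an active-dose time in only one of the three fenebrutinib arms. In the two QD arms the visit record times four placebo tablets, and the dose that determines the measured concentration was taken the morning before.

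The eDiary sentence does not fully settle the matter. Its parenthesis could mean a clock time qualified by half-day, or only a half-day label. Footnote g of Appendix 1 uses similar shorthand for diary sessions: "Patient is to complete the eDiary twice daily, approximately every 12 hours (a.m./p.m.), every day for the duration of the study". Appendix 3 as printed shows no study-drug question.

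A clock time that is never collected cannot be recovered. At stake would be the precision of exposure estimates at two of the three dose levels, and hence of the exposure-response work meant to inform later dosing.

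**Working it through.** **Which dose is timed, and what it contains.** Tablets are 50 mg (Section 4.3.1.1). From Table 3:

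| Arm | a.m. active | p.m. active | Daily active | Tablets per slot |
|---|---|---|---|---|
| 50 mg QD | 1 × 50 = 50 mg | 0 mg | 50 mg | 1 + 3 = 4; 0 + 4 = 4 |
| 150 mg QD | 3 × 50 = 150 mg | 0 mg | 150 mg | 3 + 1 = 4; 0 + 4 = 4 |
| 200 mg BID | 4 × 50 = 200 mg | 200 mg | 400 mg | 4 + 0 = 4; 4 + 0 = 4 |

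Table 3 is internally correct. On Day 8 the sample precedes the in-clinic dose, and on Day 57 dosing ended the evening before. The dose timed by the site is therefore nominally 12 h before the sample in every arm. The last active dose is nominally 12 + 12 = 24 h before it in the QD arms and 12 h in the BID arm. Day 1 precedes any dosing and is unaffected.

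**How many samples could be touched.** With about 30 patients per arm and 10% dropout by Day 57 (Section 6.1.2), and none assumed by Day 8, the QD arms give 60 + 0.9 × 60 = 114 samples. All three fenebrutinib arms give 90 + 0.9 × 90 = 171. So 114 of 171 is a ceiling, reached only if the eDiary holds no clock times.

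**What a missing clock time would cost.** The visible text gives neither a half-life nor a spread of dose times, so both are assumed. Take a one-compartment bolus model at steady state, dosed every 24 h, with fixed volume and the elimination rate k solved from one pre-dose concentration:

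- f(k, t) = exp(−kt) / (1 − exp(−24k)), with k = ln 2 / half-life.
- If the true interval is t but 24 h is used, solve f(k′, 24) = f(k, t). Estimated AUC divided by true AUC is k / k′.

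| Half-life | t = 21 h | t = 23 h | t = 25 h | t = 27 h | Mean ratio, SD 1.5 h | Added CV, SD 1.5 h |
|---|---|---|---|---|---|---|
| 4 h | 1.14 | 1.043 | 0.961 | 0.89 | 1.005 | 6.2% |
| 8 h | 1.12 | 1.038 | 0.965 | 0.90 | 1.003 | 5.4% |
| 12 h | 1.10 | 1.032 | 0.969 | 0.91 | 1.002 | 4.6% |
| 24 h | 1.07 | 1.021 | 0.979 | 0.94 | 1.001 | 3.1% |

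The last two columns come from 3,000 normal draws of the timing error; repeating the draws moves them only slightly. A deviation of 1 h costs about 2 to 4% in one patient's AUC, and 3 h about 6 to 14%. Across patients the errors nearly cancel.

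**Set against ordinary variability.** If between-patient CV is 30% (assumed), adding 6.2% gives √(30² + 6.2²) = 30.6%. At 50% it gives √(50² + 6.2²) = 50.4%. Averaging two pre-dose samples with independent timing errors reduces 6.2% to 6.2/√2 = 4.4%, and 3.1% to 3.1/√2 = 2.2%.

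**The error that would matter.** Treating the evening placebo dose as active in a QD arm would change the predicted concentration by 2^(12/half-life): 8.0 at 4 h, 2.8 at 8 h, 2.0 at 12 h and 1.4 at 24 h. It would require an analyst who knows the arm to ignore Table 3.

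**The case for a change.** The strongest case for a change is that it is cheap and the loss would be irreversible. One extra dose-time field at the pharmacokinetic visits, asked in every arm, would keep the blind and remove the doubt. The plan plainly values clock times, since Section 4.4.2.1 says antacid use "should be recorded as concomitant medications, including the date and time of last administration". Pre-dose concentrations also respond sharply to timing: a 21 h interval raises them by 19% (half-life 12 h) to 68% (4 h) relative to 24 h, and a 27 h interval lowers them by 16% to 41%.

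Part of this stands. The visit record does time a placebo dose in the QD arms, and Section 4.3.2.2 could be plainer about clock time.

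The rest does not carry. The 19 to 68% and 16 to 41% figures are real changes in concentration caused by off-schedule dosing. Recording the time does not alter the measured value; it only helps a model interpret it, and the AUC ratios above measure that benefit. Nor is the silence of Appendix 3 evidence of a gap. Section 4.5.9.1 says the eDiary covers study medication compliance, yet no such item is printed, so the printout is not the whole instrument. The fields of the Study Drug Administration eCRF are not shown, parts of Section 6.6 and of the Appendix 1 footnotes are redacted, and detailed methods are left to the Data Analysis Plans. The antacid record raises no separate issue: its time can be paired with the eDiary dose times on the same terms.

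**Conclusion.** No change to the plan follows. The observation about the visit record is right, but no defect is shown. On its natural reading, Section 4.3.2.2 already has patients record the time of each dose, morning doses included, in both cohorts. On the less favourable reading, the analyst derives time since the last active dose from Table 3 and uses the nominal 24 h.

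The cost would then be about 3 to 6% added CV in an individual's AUC and at most 0.5% mean bias, confined to the two QD arms of Cohort 2. Those figures assume the one-compartment model above, half-lives of 4 to 24 h, and symmetric dose-time scatter with a standard deviation of 1.5 h. Wider or one-sided scatter would raise them, but the documents give no ground for assuming either. The concentration summaries by visit need no time since dose, the exposure-response work may be reported separately, and the UAS7 analyses are untouched. This is a detail of data capture that the diary specification and the analysts can settle without altering the protocol.
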